**D. Description, Risks, Justification of Procedures and Data Collection Tools:**

Discomforts and other possible risks include:

**Common Risks:**

- Tiredness or boredom when completing study assessments.

**Uncommon Risks:**

- Tension or nervousness may occur from completing the study assessments. Participants can talk with the researchers about such problems, and can terminate the study if they wish.
- Problems with pain management. Only patients who are predicted to require approximately half or less than the usually prescribed opioid dose (i.e., those taking equal or less than 22.5 MME in the 24 hours prior to discharge) will be eligible. Patients will be randomized to have their provider receive a suggestion for a reduction of opioid dose versus standard of care. Providers may still choose to prescribe a higher dose as clinically indicated. The prescription tool will only make a suggestion. We will track the recommendation made as well as the actual dose prescribed.

We will follow up with all patients at half of their usual follow-up period (usually 2 weeks) via a REDCap survey, phone, email, or in clinic to assess how they are doing and if they are likely to run out of opioid medications despite still requiring them for acute surgical pain. For patients, who are running low on opioid pain medications, we will arrange for additional pain medications to be prescribed as deemed appropriate by their providers using the electronic prescription route if needed. We will monitor the study progress closely and reassess our study design

if more than 5 intervention group patients require prescriptions prior to scheduled clinic follow-up.

All patients are routinely given a phone number where they can reach a surgical provider 24 hours a day, seven days a week, in case pain therapy is inadequate.

The study team will monitor need for secondary prescriptions from providers to ensure that no significant under-prescription of opioid medications after surgery occurs.

These recommendations are in accordance with current quality improvement efforts by the system-wide Pharmacy and Therapeutics (P&T) Opioid Subcommittee charged with addressing UCHealth actions to meet the new Joint Commission Pain Assessment and Management guidelines. This committee is co-chaired by the Co-I of this study ([name]) and [name], Pharm.D. The PI is also an active member of the system-wide UCHealth Opioid and Pain Management Steering Committee that is chaired by [name]. This committee also supports this application. Lastly, the PI holds an active funded 5-year NIH K23 grant "*Improving Opioid Prescription Safety After Surgery*" that provides material and personal support, statistical support, and regulatory support for this application.

**Rare But Serious Risks:**

- Breaches of confidentiality.

Confidentiality is maintained throughout the study's entirety and protected health information will not be disclosed outside the University of Colorado. The study therefore does not involve any more than minimal risk to patients, namely loss of confidentiality. While there is no direct benefit to subjects, knowledge gained from our study will help to tailor prescription of analgesic medications after surgery to patients' actual needs.

Strict safeguards for data protection will be followed including storage on protected servers, password protection and monitored access to authorized users. Please see the Data and Safety Monitoring Plan section for additional details. Patients are provided with the PI's office phone number, COMIRB's phone number, and the PI's email address and phone number should they have any questions. Patients may withdraw from the study at any time.

**Data and Safety Monitoring Plan:**

Each participant will be assigned a corresponding study ID number. ID numbers will be assigned in the order of patient enrollment. A master list connecting the enrollment number with the patient's medical history number will be maintained only for the duration of the data collection. Only PI-approved study personnel who have current COMIRB-required human subject protection training will have password-protected and monitored access to the data. Following the interpretation of the data, the master list will be destroyed and no patient identifying information will be maintained.

Demographic data, information on prescribed and non-prescribed medications, and clinical outcome values relevant for pain management will be obtained from the Epic database and stored in a secure fashion using REDCap.

**E. Potential Scientific Problems:**

Concomitant provider education may itself lead to a change in pain management practices. To address this, a future larger pragmatic clinical trial could include cluster randomization based on study site. Few prognostic models actually are in clinical use, often because they have not been externally validated and because of the data collection burden. Our local Clinical Decision Support Program has confirmed the feasibility of our proposal to integrate a future decision-making tool into the electronic medical record and order entry system.

**F. Data Analysis Plan:**

The intent-to-treat (ITT) sample is defined as those who complete at least one survey. In our prior observational study, 100% of the C-section patients satisfied this criterion. If there is a subsample that does not complete at least one survey, we will compare that group to the ITT group on relevant demographic and clinical characteristics. Outcomes not requiring any response to the survey will be compared for all patients enrolled, regardless if they completed at least one survey.

The prescription tool and prescription as usual (PAU) groups will be compared on baseline demographic and clinical characteristics using Mann-Whitney tests, independent t-tests and chi-square tests as appropriate for continuous and categorical data; when necessary (i.e. when variables have distributions violating assumptions), nonparametric procedures will be substituted. We expect randomization to ensure group equivalence; should variables be different they will be evaluated as covariates in the analyses described below as appropriate.

Our primary analyses will compare the prescription tool group with the PAU group on oral morphine equivalent dose left over (not used) from the total amount of prescribed opioids. Based on our preliminary data, we will assume the control group to receive an opioid prescription for 20 oxycodone 5mg tablets (150MME), leading to a mean MME of 101.8 (SD 60.5) left over. Conservatively estimating a 50% adoption rate of the decision support tool by prescribing clinicians, we would expect a mean MME of 55 (SD 37.6) left over opioids in the intervention group. Assuming statistical comparisons will be made using Mann-Whitney test a sample size of n=22 per group (44 total using 1:1 allocation) will yield 90% power with an assumed one-tailed alpha of 0.05 (G-Power, version 3.1.9.2).

For the primary weekly opioid use variable and for secondary longitudinal variables of interest (i.e. weekly scores for pain interference and pain intensity), trajectories will first be visually compared between the two groups. Mixed models will then be used to analyze each outcome that will include fixed group, time, and group by time interaction effects and random patient effects. Covariates will only be included if they differ by group at baseline and are related to the outcome of interest. The test of the group by time interaction will indicate if each outcome differs over time by groups. Overall means for each outcome will be estimated and compared between groups as will week 1 and week 4 means of each outcome will be separately compared between groups. These analyses on the ITT sample will then be repeated on the subset of patients who complete all 4 surveys and any differences between results will be reported.

Important secondary summary variables that will be compared between groups using chi-square, t-test, nonparametric, and covariate-adjusted (i.e. ANCOVA) methods as appropriate are: need for additional opioid prescriptions (yes, no), and amount of opioid and non opioid analgesic drugs taken (total mg). Reported medication disposal by group will additionally be described.

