### III. Preliminary Studies/Progress Report:

**Preliminary Studies.** In a cohort of 652 patients who had undergone surgery at UCH Metro clinicians chose the same cumulative opioid dose (300 oral morphine equivalents) in more than 75% of patients for the discharge opioid prescription (Figure 1). These data indicate that opioids following inpatient surgery are not prescribed in an individualized fashion, but rather that most patients receive a very similar regimen for post-discharge pain management. Using the same EHR (Epic) database that generated the data above, we are able to generate information on types and doses of pain medications that are administered to patients, who are still in the hospital in real time ([name], Chief Medical Information Officer and [name], CMO at UCHHealth strongly support this project). We have previously shown that 83% of patients after Cesarean section and 71% of thoracic surgery patients report taking half or less of opioids prescribed; 53% and 45% respectively report taking five or less of the prescribed pills. Hence, a “one size fits all” approach to pain management after discharge is common in clinical practice and leads to frequent over-prescription of opioids. Based on our own preliminary data and recommendation published by others, opioids taken 24 hours prior to discharge inform the amount of opioids that are likely to be used at home and hence the following prescriptions amounts have been suggested for patients taking equal or less than 22.5 MME in the 24 hours prior to discharge:

[figure not shown]

Figure 4: Cumulative opioid dose in oral morphine equivalents (OME) prescribed to 652 patients upon hospital discharge after surgery. Clinicians chose the same cumulative opioid dose (300 OME) in more than 75% of patients.

- no opioids for home use for patients having taken no opioids in the last 24 hours prior to discharge
- 75 morphine milligram equivalent (MME), e.g. 10 oxycodone 5mg tablets, for home use for patients having taken equal or less than 22.5 MME, e.g. 1-3 oxycodone 5mg tablets in the last 24 hours prior to discharge.

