We will seek a waiver of written consent for surveying providers who are given the dosing suggestion via the EHR-based Prescription Tool. At their convenience, these providers will complete an online postcard consent and survey via REDCap.

After consent, demographics and the best contact information will be collected (remotely by phone during the COVID-19 pandemic or as required by UCHealth) from those enrolled patients who indicate they are interested in completing the surveys after their hospital discharge.

We expect 44 patients to complete all four weekly surveys and we define the intent-to-treat sample as patients who complete one or more surveys (providing at least one observation to be used in analyses). To conservatively allow for increased variability due to attrition, 60 patients will be randomized equally electronically to intervention (prescription tool) or no intervention (prescription as usual). We will use an electronic randomization scheme created so that the principal investigator and statistician can remain blind to assignment.

At the time of writing the prescription for a patient the provider will be informed that a patient may be considered for a lower post-discharge opioid dose (No opioids for patients who did not take any opioids in the last 24 hours, and 10 oxycodone 5mg tablets, for patients having taken less than 22.5 MME, e.g. 1-3 oxycodone 5mg tablets in the last 24 hours). No dosing recommendations for patients having taken more than 22.5 MME will be made as these patients are not eligible for this study. Final dosing decisions and drug choices will remain at the discretion of the treating provider and decisions will be tracked.

For this pilot study, the provider information (best practice alert – BPA) will be operationalized via a written recommendation on paper handed to the provider by study staff in a sealed envelope or emailed with a read receipt that the provider will be asked to open and read. Alternatively, the BPA may be presented electronically using a screen. Providers will be asked to acknowledge that they read the BPA by closing the window or opening the envelope or email.

For the intervention group:

For patients receiving no opioids in the last 24 hours prior to an oxycodone or oxycodone/acetaminophen discharge prescription being written:

**BPA: “In the last 24 hours, your patient received NO opioids. Consider not prescribing any opioids for pain management after discharge.”**

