For patients receiving >0 MME up to ≤22.5 MME in the last 24 hours prior to an oxycodone or oxycodone/acetaminophen discharge prescription being written (example BPA is for 15 MME – 2 oxycodone 5mg tablets):

**BPA: “In the last 24 hours, your patient received opioid medication equivalent to 2 oxycodone 5 mg tablets by mouth. Consider writing for a total of 10 oxycodone 5 mg tablets for pain management after discharge.”**

Note, oxycodone-containing medications are the opioid prescribed in >96% of cases after Cesarean section at our hospital. We will make equivalent recommendations if hydrocodone is used. Based on our data, no other opioid medications have been prescribed for use after discharge following Cesarean section.

For the control group:

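### The intervention-arm SD of 37.6 MME is attributed to 50% adoption without a derivation and does not fit the plan's own prescribing figures; on the plain reading, power at 22 per group is about 78%, not the stated 90%

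*Combined protocol and SAP*

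**What the plan says.** Section F (Data Analysis Plan) takes the control values from preliminary data. A control prescription is 20 tablets, or 150 MME, "leading to a mean MME of 101.8 (SD 60.5) left over". For the intervention arm it says: "Conservatively estimating a 50% adoption rate of the decision support tool by prescribing clinicians, we would expect a mean MME of 55 (SD 37.6"). It concludes that "a sample size of n=22 per group (44 total using 1:1 allocation) will yield 90% power with an assumed one-tailed alpha of 0.05", using the Mann-Whitney test. This is the plan's only power statement.

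The recommendation has two tiers. Section III gives the lower as "no opioids for home use for patients having taken no opioids in the last 24 hours prior to discharge". For patients with some use, up to 22.5 MME, the alert in section C reads "Consider writing for a total of 10 oxycodone 5 mg tablets for pain management after discharge", which is 75 MME.

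The recommendation does not bind. Section C says "Final dosing decisions and drug choices will remain at the discretion of the treating provider and decisions will be tracked", and the risk section adds "Providers may still choose to prescribe a higher dose as clinically indicated". The risk section also says that both the recommendation and the dose prescribed will be tracked.

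On numbers, section C says that "60 patients will be randomized equally electronically to intervention (prescription tool) or no intervention (prescription as usual"). One completed survey is enough to enter the analysis set.

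**The concern.** Fifty per cent adoption most naturally means that half the intervention patients are prescribed as the tool recommends and half as usual. The second half then resembles the control group, with left-over mean 101.8 and SD 60.5. An arm that mixes such patients with others who leave little or nothing should be at least about as variable as the control arm. The plan instead gives it a much smaller SD, 37.6 against 60.5.

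A smaller SD raises the standardised difference, so any error here flatters the power. The plan does not define adoption. It does not give the share of patients expected in each tier, or say what non-adopted patients are assumed to be prescribed. A reader therefore cannot check the figure, and calling the adoption estimate conservative suggests a safety margin that is nowhere shown.

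**Working it through.** **Inputs from the plan.** Control 101.8 (SD 60.5) on 150 MME; intervention 55 (SD 37.6); adoption 50%; recommended amounts 0 or 75 MME; one-tailed alpha 0.05; 22 per group, with 60 randomized, so at most 30 per group.

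**1. Reproduce the stated power.** Difference = 101.8 − 55 = 46.8. Pooled SD = √((60.5² + 37.6²)/2) = 50.37. d = 46.8/50.37 = 0.929. The usual Mann-Whitney approximation multiplies n by 3/π (normal parent) and uses a noncentral t.
- n = 22: noncentrality 3.01 on 40.0 df, power 90.6%.
- n = 30: noncentrality 3.52 on 55.3 df, power 96.6%.

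The plan's 90% is reproduced.

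**2. Smallest SD under need-independent adoption.** If a random half keeps the control distribution, the arm's variance is

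0.5 × 60.5² + 0.5 × (adopter SD)² + 0.25 × (gap between the two means)².

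The first term alone gives SD ≥ √(0.5 × 60.5²) = 42.8 at any mean. For an arm mean of 55, adopters must average 2 × 55 − 101.8 = 8.2, so the gap is 93.6. With adopter SD set to zero, SD ≥ √(0.5 × 60.5² + 0.25 × 93.6²) = 63.4. If adopters' left-over amounts must also come from the 0 and 75 MME tiers, a linear program over all use distributions matching the control mean and SD (7.5 MME steps) gives a minimum of 64.1.

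**3. Smallest SD if adoption depends on use.** The same linear program, with adopters chosen freely by use and the arm mean held at 55:

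| Non-adopted prescription (MME) | Minimum SD, adoption selected by use | Minimum SD, adoption independent of need |
|---|---|---|
| 150 (the plan's usual amount) | 43.2 | 64.1 |
| 135 | 37.5 | 55.0 |
| 120 | 32.7 | 46.3 |

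At 150 MME, 37.6 is out of reach in both columns. The 135 and 120 rows are sensitivity values only.

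**4. Power on the plain reading, by the plan's formula.** At mean 55 and SD 63.4, d = 46.8/√((60.5² + 63.4²)/2) = 0.755.
- n = 22: noncentrality 2.45, power 77.7%.
- n = 30: noncentrality 2.86, power 88.1%.

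**5. Power by simulation.** Assumptions: use is unchanged by the prescription; control left-over is Beta-shaped on 0 to 150 MME and matched to 101.8 (SD 60.5); left-over is the prescribed amount minus use, not below zero; half adopt at random; non-adopters receive 150 MME.

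| Share in the 0 MME tier | Arm mean | Arm SD | Power, n = 22 | Power, n = 30 |
|---|---|---|---|---|
| 0% | 73.7 | 56.8 | 49% | 60% |
| 50% | 62.2 | 62.9 | 68% | 79% |
| 82% | 55.0 | 65.6 | 78.5% | 88.7% |
| 100% | 51.0 | 66.7 | 84% | 93% |

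Under these assumptions, a mean of 55 itself needs about 82% of patients in the 0 MME tier, a share the plan does not give. Over three control shapes, with the tiers and unchanged use, power at or near mean 55 was about 78 to 82% at 22 per group and 88 to 91% at 30.

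**The case against.** Four points can be made for the plan.

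**Adoption is undefined, so the conflict depends on a reading.** This is true. The provider keeps discretion, so partial or need-related adoption fits the design. If every prescription moved halfway to the recommendation, simulated power at 22 per group would be 82 to 95%; with 60% in the 0 MME tier the arm would be 55.8 (SD 42.7), with 91% power. Adoption selected by use, with non-adopters at 150 MME, gave 89% at mean 56.8 (SD 43.1). With non-adopters at 135 MME, need-independent adoption gave 83 to 99%. So about 90% is attainable, but each route needs an assumption that the plan does not make.

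**The 78% is not a ceiling.** A reader might take it as an upper limit on power. It is a limit only within the normal-parent formula at mean 55. The mixture is bimodal, and Mann-Whitney power depends on its shape: shapes not tied to the tiers gave about 59 to 94%. The high values (90% and above) came from setting every adopter to about 8.2 MME left over, or from a control distribution that exceeds the 150 MME cap. With the actual tiers and unchanged use, the highest value at 22 per group was about 86%.

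**More than 22 per group may be analysed.** This stands. One survey suffices, and the plan reports that all its earlier Cesarean patients met that criterion. Near 30 per group, the plain reading at mean 55 comes close to 90%. The stated claim, however, is for 22.

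**It is a pilot.** This bears on how much work the remedy deserves. It does not supply the missing derivation.

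**Conclusion.** The point holds in a limited form. The SD of 37.6 has no derivation and cannot arise at mean 55 from 50% adoption of the 0/75 MME recommendation when the rest stay at 150 MME. The minimum there is about 63 to 64 if adoption is independent of need and 43.2 if it is selected by use. On the need-independent reading, power at mean 55 is about 78% at 22 per group and 88% at 30 by the plan's formula, and lower if fewer patients fall in the 0 MME tier (49% and 60% if none do). The simulated figures rest on unchanged use and on the control shapes tried.

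Two stronger conclusions are not supported. A reader might infer that the power calculation is arithmetically wrong, but 90.6% follows from the printed inputs. A reader might also infer that the trial is shown to be underpowered. The documents do not settle that, because the inputs that decide it are unstated and up to 30 per group may be analysed. What is established is that the stated adoption assumption, read plainly, does not deliver the stated power. It should be fixed, but it does not threaten the design.

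**What to change.** Revise the sample-size paragraph of section F as follows.

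- Define adoption by comparing the tracked recommendation with the dose actually prescribed.
- State the assumed prescription for non-adopted patients, the expected shares in the 0 and 75 MME tiers, and whether adoption is assumed to depend on use.
- Rebuild the intervention-arm mean and SD from those inputs. If 55 (SD 37.6) came from preliminary data, say so and show the steps.
- Restate the one-tailed Mann-Whitney power at 22 and at 30 per group, preferably by simulation, with a few alternative inputs alongside.
- Remove the word *conservatively* unless the restated figures support it.
- Do not choose an adoption rate after the fact to preserve the printed pair.

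The cost is one paragraph, a small table and a re-run of the calculation. The sample size, design, test and prescribing recommendations stay as they are. The downside is that the stated power may become less favourable.

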### I. Hypotheses and Specific Aims:

We have previously shown that 83% of patients after Cesarean section and 71% of thoracic surgery report taking half or less of opioids prescribed; 53% and 45% respectively report taking five or less of the prescribed pills. Such overprescribed opioids are stored in unsecured locations in the 75% of cases. These opioids represent a major source of potential morbidity and mortality. The *rationale* that underlies the proposed research is that once we have proven the efficacy of patient-centered pain management approaches, we can improve surgical pain therapy on a large scale.

**Specific Aim:** We will utilize the electronic health record to individualize pain therapy in surgical patients after hospital discharge using last 24-hour opioid intake as the decision variable for the amount of opioid pain pills prescribed. Our preliminary data indicate that current opioid prescription practice after surgery follows a “one size fits all” pattern. In-hospital opioid use 24 hours prior to discharge serves as a strong indicator to correctly estimate needs for analgesic medications at home. We will test our hypothesis that this tool will reduce the amount of opioid medications prescribed while maintaining patient post-operative pain control. We will test this tool prospectively for 44 post Cesarean section patients anticipated to use about half or less of the usually prescribed amount of opioid pain pills randomized equally to prescription tool intervention or no intervention (prescription as usual).

This protocol addresses only Specific Aim #3 of the original grant. Specific Aim #1 and #2 are addressed under a separate COMIRB protocol #14-1938.

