## **B. Description of Population to be Enrolled:**

### **Survey population:**

Inflating enrollment by approximately 25% to account for drop out and result in 44 patient completers, we will consent 60 adult patients receiving a Cesarean section procedure. After completing an observational study in three surgical groups (thoracic surgery, gastrointestinal surgery, C-section), we chose to evaluate this intervention first in C-Section patients based on their unique characteristics: low procedural variability, low incidences of chronic opioid use, and low level of comorbidities. Also, the issue of having potentially unsecured opioids in a household with young children is of special relevance for opioid safety research in the Cesarean section cohort.

Inclusion Criteria: 1) Women ages at least 18 years of age having undergone Cesarean section surgery at the University of Colorado Hospital are eligible. 2) Willingness to complete weekly surveys for 4 weeks after discharge. 3) Anticipated to need half or less of the usually prescribed amount of opioids based on the amount of opioids taken in the last 24 hours prior to the opioid medication being written for discharge (only patients who took 22.5 MME or less opioids in the last 24 hours prior to the day of discharge will be eligible for this study). Inclusion and exclusion criteria (including the amount of opioids taken in the last 24 hours prior to discharge) will be evaluated in the morning in patients scheduled to be discharged later that day.

Exclusion Criteria: 1) Patients under the age of 18 years, 2) Patients returning to institutional settings (e.g. prison, jail, mental health facility), 3) Pregnant women (patients will be approached after their C-section), 4) Decisionally challenged patients, 5) Blind or illiterate patients.

Based on our prior research factors such as emergency status, prior opioid use, repeat vs primary C-section, and associated procedures were not associated with post-discharge opioid use once we adjusted for last-24 hour inpatient opioid use. Hence, these patients will not be excluded.

We will perform a randomized clinical trial (RCT) of an EHR-based recommendation to prescribe opioids at discharge according to the recorded last 24-hour inpatient use according to current recommendations and evaluate its effect on the amount of opioids prescribed as well as pain control after discharge.

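### The mixed models admit a covariate only after a chance baseline imbalance; naming the last-24-hour opioid dose in advance would make the overall and week 1 comparisons of opioid use somewhat more precise

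*Combined protocol and SAP*

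**What the plan says.** Section IV.F (Data Analysis Plan) of the combined protocol and SAP introduces the mixed models with the words "For the primary weekly opioid use variable and for secondary longitudinal variables of interest". The terms fixed in advance are group, time, their interaction and a random patient effect. Any further term must pass a two-part test: "Covariates will only be included if they differ by group at baseline and are related to the outcome of interest". No significance level or other threshold for a difference is given.

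The paragraph on baseline comparisons in the same section points the same way: "should variables be different they will be evaluated as covariates in the analyses described below as appropriate". It does not bar other covariates. For the summary variables, including total opioid taken, the section allows "chi-square, t-test, nonparametric, and covariate-adjusted (i.e. ANCOVA) methods as appropriate" without naming a covariate.

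The contrasts to be reported are set out as follows: "Overall means for each outcome will be estimated and compared between groups as will week 1 and week 4 means".

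Elsewhere the protocol singles out one predictor. Section I states: "In-hospital opioid use 24 hours prior to discharge serves as a strong indicator to correctly estimate needs for analgesic medications at home". Section IV.B says that emergency status, earlier opioid use, repeat or primary section and associated procedures "were not associated with post-discharge opioid use once we adjusted for last-24 hour inpatient opioid use". Section IV.A lists this dose among the study measurements.

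**The concern.** In a randomised trial any baseline difference between arms is chance. A covariate earns its place through its relation to the outcome, whether or not it happens to be unbalanced. A rule that demands both conditions discards a good predictor in most trials. It also leaves the choice of model until the data have been seen, with no stated criterion.

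The rule covers the variable on which the whole intervention is built, and for which the team adjusted in its own earlier research. At stake is precision only. It concerns the overall and week 1 group differences in weekly opioid use, which the mixed-model paragraph calls primary, and total opioid taken if that comparison is left unadjusted.

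**Working it through.** **1. The plan's own sample size.** Section IV.F gives leftover MME of 101.8 (SD 60.5) and 55 (SD 37.6).
- Pooled SD = sqrt((60.5² + 37.6²)/2) = 50.37, and d = 46.8/50.37 = 0.929.
- For the Mann-Whitney test (asymptotic relative efficiency 3/π, one-sided 0.05), 22 per group gives 90.6% power, and 22 is the smallest n reaching 90%.

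The stated figure reproduces. It rests on an unadjusted test of leftover opioid, so the covariate rule does not affect it.

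**2. How often the rule lets the dose in.** Under randomisation a baseline test rejects at about its own level, so that level is roughly the ceiling on inclusion. The threshold is not stated; 0.05 and 0.20 were assumed. In simulation (Mann-Whitney test on dose, adjusted t test on total use, r = 0.2-0.46), the dose entered in 1.6-4.9% of trials at 0.05 and 12.1-20.3% at 0.20. It was therefore left out in about 80-98%.

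**3. Gain by formula.** Let r be the correlation of dose with home use among eligible patients. The documents give no value; 0.2-0.46 is assumed. Against an unadjusted comparison, and net of the lost degree of freedom, variance reduction = 1 − (1 − r²)(1 + 1/(N − 4)).

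| r | N = 60 | N = 44 |
|---|---|---|
| 0 | −1.8% | −2.5% |
| 0.2 | 2.3% | 1.6% |
| 0.3 | 7.4% | 6.7% |
| 0.46 | 19.8% | 19.2% |

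Example, N = 60 and r = 0.46: 1 − 0.7884 × 1.0179 = 0.198. The standard error falls by 1-10% over r = 0.2-0.46. Break-even is r² = 1/(N − 3), so r is about 0.13 (N = 60) or 0.16 (N = 44).

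**4. The entry limit.** Section IV.B admits only patients at 22.5 MME or less, which narrows the dose range. With R the unrestricted correlation and u the ratio of dose SDs, r = Ru/sqrt(1 − R² + R²u²). For an assumed u = 0.5, r = 0.2 and 0.46 need R = 0.38 and 0.72. The break-even values need R = 0.25-0.31.

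**5. Simulation with the tool's rule built in.** This matters because section IV.C ties the recommended quantity to the same dose ("No opioids for patients who did not take any opioids in the last 24 hours", and a fixed small supply otherwise).
- Assumptions: 20,000 trials per setting; 22 or 30 per arm; adoption 50% or 80%; 30% or 50% of patients at zero dose; doses 0, 7.5, 15 and 22.5 MME; gamma-distributed need (shape 0.6, mean 48 MME) capped at the quantity prescribed; weekly need shares of 60/25/10/5% or equal.
- The value of r was set in the control arm, and the dose slope was free to differ by week.

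| Variance reduction | r = 0.2 | r = 0.3 | r = 0.46 |
|---|---|---|---|
| Overall or total use | 3-8% | 9-14% | 19-25% |
| Week 1 | 2-8% | 5-13% | 10-22% |

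Week 4 changed by −2% to +5% across all settings. At r = 0 the largest loss was 2.8%.

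Random-intercept REML fits with declining use and 0% or 15% of weeks missing agreed: an overall gain of 4-5% at r of about 0.2 and 15-19% at about 0.41, and −2.8% to +4.0% at week 4.

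**6. Form of the adjustment.** If use declines and a single dose slope is shared by all weeks, week 4 variance rises by 38-63% at r = 0.2 and by 130-173% at r = 0.46. Slopes by week avoid this. Adjusting leftover MME for dose changes its variance by only −3% to +6%.

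**The case against.** The strongest reply is that the benefit is small and its size is assumed. The documents give no correlation. The phrase in section I rests on a cited study whose title concerns the amount prescribed, not the amount used at home. The prior research mentioned in section IV.B is not said to be limited to low-dose patients, and r = 0.46 asks for a demanding unrestricted correlation. With an unrestricted 0.5 and the dose SD cut to 40-60%, r is 0.23-0.33. At N = 44, r = 0.2-0.3 would move 80% power only to 81-83%. **This stands**, and it makes the lower half of the range the more plausible.

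The week 1 upper figure may also be generous. In a random-intercept model with intraclass correlation 0.5 and the dose explaining 25% of between-patient variance, the week 1 SE ratio is 0.947, about 10% of variance (1 − 0.947² = 0.103). **This stands as a caution.**

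The percentages compare adjustment with no adjustment. A loose screen at 0.20 would recover roughly half to two-thirds of the gain in estimator variance; one at 0.05 recovers about a quarter or less. **This stands**, but whenever the screen excludes the dose, the reported interval keeps its unadjusted width.

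The trial is sized on leftover opioid, and the group-by-time test gains nothing from a shared slope. **Both are true**, and no gain is claimed for either.

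A linear dose term may fit poorly where the recommendation steps up after zero, and the dose-use relation may differ by arm. A poor fit costs precision and does not bias a randomised comparison. The simulated gains already include the stepped, arm-specific cap on use.

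Finally, ANCOVA is already allowed for total opioid taken. There, only the covariate's name is missing.

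**Conclusion.** The concern holds. The rule for the mixed models is exclusive, the dose is not exempted, and the plan's own reasoning identifies it as the covariate to use. The cost is precision alone. By formula it is 2-20% of variance for overall or total use if r among eligible patients is 0.2-0.46, with smaller gains at week 1 and none claimed at week 4, for pain scores or for leftover opioid. These figures depend on an assumed r, an assumed screening threshold and assumed outcome distributions. The gain is slight if r is about 0.2 or less, and turns into a small loss below about 0.13-0.16. There is no bias and no effect on the stated 90% power. This is a worthwhile, cheap improvement and does not threaten the trial's validity. Confidence in its size is moderate.

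**What to change.** - In section IV.F, delete the condition that a covariate must differ at baseline. Reword the baseline paragraph so that group comparisons are descriptive and do not select covariates.
- In the mixed model for weekly opioid use, prespecify last-24-hour inpatient MME (linear) as a fixed covariate regardless of balance, with a dose-by-week term so that its slope can fall as use falls.
- Name the same covariate in the ANCOVA of total opioid taken.
- Leave the Mann-Whitney test on leftover MME as it is, and add no dose-adjusted leftover analysis.

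The cost is SAP wording, one covariate with its week term and one degree of freedom per weekly contrast. No new data are needed. The downside is the 2-3% of variance lost if the dose proves unrelated to use.
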